9.8. Quality Control

Data in Optum's claims database are collected monthly in an electronic format. Analyses are programmed according to the specifications in the protocol and documented in a programming plan. All analyses will be performed internally and according to Pfizer analytic standards, including double programming to ensure quality control. All quality checks are documented in the programming plan.

9.9. Limitations of the Research Methods

There are several limitations associated with this study. This analysis is from one insurer that provides employer-sponsored and Medicare Advantage coverage and thus may not generalize to other populations, such as traditional Medicare fee-for-service, other government insurance or uninsured. It is possible that some vaccines may be missing if patients received vaccine in a setting where an insurance claim was not filed (ie employer sponsored clinic or paid out of pocket). This may be more problematic for influenza vaccine for younger ages. This will only impact the singular vaccine groups (ie, COVID-19 alone or influenza alone). The healthcare claims data are collected for billing purposes and may be subject to misclassification, misdiagnosis, and underreporting. Additionally, for our medically attended COVID-19 endpoints, we do not have laboratory confirmation of the COVID-19 diagnosis, therefore it is possible that some patients are being diagnosed with symptoms alone or that we are missing positive cases due to at-home testing.

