8. RESEARCH QUESTION AND OBJECTIVES

Primary Objective 1: To describe the proportion of Pfizer-BioNTech bivalent mRNA COVID-19/influenza vaccines that are concomitantly administered, and the characteristics of patients who receive concomitant administration.

Primary Objective 2: To estimate vaccine effectiveness (VE) of concomitant administration of a single dose of the mRNA Pfizer-BioNTech bivalent COVID-19 vaccine and a licensed flu vaccine versus either vaccine alone against all-cause hospitalization or acute respiratory illness requiring hospitalization, emergency department/urgent care or outpatient encounters.

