9.3. Variables

9.3.1. Exposure

Table 1. Vaccination Status Variables		
Variable	Role	Operational definition
Group 1: Same Day (Concomitantly administered Pfizer-BioNTech COVID-19 mRNA bivalent vaccine + influenza vaccine)	Exposure	
Patients meeting the following criteria will be included in the Same Day cohort:
 
1. NDC or CPT codes for both the Pfizer-BioNTech mRNA bivalent COVID-19 vaccine and an influenza vaccine during the study period.2. The first Pfizer-BioNTech mRNA bivalent COVID-19 vaccine and influenza vaccine NDC or CPT codes during the study period occurred on the same date.3. No influenza vaccine NDC or CPT code between 01 August 2022 and 30 August 2022. 
If the patient receives >1 mRNA bivalent COVID-19 vaccine or influenza vaccine during follow-up, the patient is censored on the date of the NDC or CPT code for the second vaccine of the same type. mRNA bivalent COVID-19 and influenza vaccine NDC and CPT codes are listed in Appendix Table 1.

Group 2: COVID alone (COVID-19 mRNA bivalent vaccine alone)	Exposure	
Patients meeting the following criteria will be included in the COVID-19 alone cohort:
 
1. Pfizer-BioNTech mRNA bivalent COVID-19 vaccine NDC or CPT code during the study period and no influenza vaccine on that date.2. No influenza vaccine NDC or CPT code between 01 August 2022 and 30 August 2022. 
If the patient receives >1 mRNA bivalent COVID-19 vaccine (any type) during follow-up or an influenza vaccine, the patient is censored on the date of the NDC or CPT code for the second mRNA bivalent COVID-19

PFIZER CONFIDENTIAL

Table 1. Vaccination Status Variables

Variable	Role	Operational definition
		vaccine/influenza vaccine. mRNA bivalent COVID-19 vaccine NDC and CPT codes are listed in Appendix Table 1 .

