Prior diabetes	Patient Characteristics	Any code (any setting) within the 1 year baseline for diabetes
Prior kidney disorders	Patient Characteristics	Any code (any setting) within the 1 year baseline for kidney disorders
Month of index date	Patient Characteristics	August/September, October, November, December, January (Note: August will be combined with September as only 1 day of August will be included in the cohort). Model specification: categorical
Prior Influenza vaccination	Patient Characteristics	One claim (NDC or CPT) for influenza vaccine of any type measured between 31 August 2021 – 31 May 2022 Model specification: dichotomous (yes/no)
COVID-19 vaccination in the 1 year prior	Patient Characteristics	One claim (NCD, CPT, procedures) for COVID vaccine of any type in the 365 days before index separated into the following time periods: 
 Recent vaccination: ≤ 60 days prior to index Older vaccination: Between 61 and 365 days prior to index No evidence of vaccination in the prior year If there is evidence of >1 COVID vaccination in the 365 days prior to index, patients are categorized using the date of the most recent dose administered during the baseline period. Model specification: categorical (3 level)
Time from last COVID-19 vaccine dose (Due to the likelihood of misclassification, this variable will be used for descriptive table only, not for model)	Patient Characteristics	Number of days from last COVID-19 vaccine dose. Reported as categories: ^{17,18} <60 days, 60-179, ≥ 180 , not applicable. Continuous statistics including mean, standard deviation (SD), median (Q1-Q3), minimum, and maximum, among those with a prior dose.
Monovalent mRNA COVID-19 vaccine in the 60 days prior to index (Note for descriptive table only, not for model due to collinearity with covid vaccine in the prior year above)	Patient Characteristics	Yes/No. One claim (NCD, CPT, procedures) for monovalent mRNA COVID-19 vaccine between 01 July 2022 – 30 August 2022

PFIZER CONFIDENTIAL

Table 4. Covariates

Variable	Role	Operational definition

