9.5. Study Size

The sample size for this study is fixed by the duration of the observation window. All subjects who meet the inclusion/exclusion criteria will be included in the analyses.

Feasibility analyses from 31 August 2022- 16 January 2023 confirmed the availability of data to identify vaccinated subjects. Table 5 below shows the estimated number of patients in each group.

Table 5. Estimated Number of Patients in Each Vaccination Exposure Group

	Group 1: Same Day	Group 2: COVID- 19 alone	Group 3: Flu alone	CCl [REDACTED]
18-64	244,864	144,695	772,418	CCl [REDACTED]
65+	382,806	225,842	1,351,093	CCl [REDACTED]

Composite COVID-19 hospitalizations/UC/ED

For 65+, and the Group 1 vs Group 2 comparison of the COVID-19 related composite hospitalizations/ED/UC endpoint, we assume the percentage of patients in Group 1 will be 63% and the expected percentage of patients in Group 1 and Group 2 with an event overall will be 0.56%. If we use a non-inferiority margin of 1.15 for the upper bound of the 95% CI, 1-sided alpha of 0.025, and 80% power, and an expected HR of 1, then we would need 1,724 events resulting in 193,548 patients in Group 1, and 113,671 in Group 2, which meets our current estimated sample size.¹⁹

For 18-64, and the Group 1 vs Group 2 comparison of the COVID-related composite hospitalizations/ED/UC endpoint, we assume the percentage of patients in Group 1 will be 63% and the expected percentage of patients in Group 1 and Group 2 with an event overall will be 0.066%. If we use a non-inferiority margin of 1.15 for the upper bound of the 95% CI, 1-sided alpha of 0.025, and 80% power, and an expected HR of 1, then we would need 1,638,003 in Group 1, and 962,002 in Group 2, which does not meet our current estimated sample size.

Composite influenza hospitalizations/UC/ED

For 65+ and for the Group 1 vs Group 3 comparison of the flu-related composite hospitalizations/UC/ED endpoint, we assume the percentage of patients in Group 1 will be 23% and the expected percentage of patients in Group 1 and Group 3 with the endpoint overall will be 0.3%. If we use a non-inferiority margin of 1.15 for the upper bound of the 95% CI, 1-sided alpha of 0.025, and 80% power, and an expected HR of 1, then we would need 2,269 events resulting in 176,179 in Group 1, and 589,817 in Group 3, which meets our current estimated sample size.

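### Section 9.9 treats unclaimed vaccines as a matter for the single-vaccine groups only, but those groups are the comparators in every model, so the HRs (mainly Same day vs COVID alone) and the Objective 1 proportion are affected

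*Combined protocol and SAP*

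**What the plan says.** All references are to the combined protocol and SAP.

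- **Section 9.9** states the limitation: "It is possible that some vaccines may be missing if patients received vaccine in a setting where an insurance claim was not filed". It names employer clinics and out-of-pocket payment as sources, adds "This may be more problematic for influenza vaccine for younger ages", and closes with "This will only impact the singular vaccine groups (ie, COVID-19 alone or influenza alone". It gives no rate, no direction of bias and no consequence for either objective.
- **Section 9.3.1, Table 1** puts a patient in Group 1 only with "NDC or CPT codes for both the Pfizer-BioNTech mRNA bivalent COVID-19 vaccine and an influenza vaccine during the study period", the first of each falling on the same date. Group 2 needs "Pfizer-BioNTech mRNA bivalent COVID-19 vaccine NDC or CPT code during the study period and no influenza vaccine on that date". Group 3 is the mirror image for influenza vaccine.
- **Section 9.5** bases every sample-size calculation on a "non-inferiority margin of 1.15 for the upper bound of the 95% CI", with one-sided alpha 0.025, 80% power and an expected HR of 1.
- **Section 9.7** lists only models of Same day against COVID-19 only or Flu only. The visible sensitivity analysis adds censoring at antiviral dispensing. Missing data are not imputed. Section 9.3.2 aims the negative control outcomes at confounding by health-seeking behaviour.
- **Section 8** sets Objective 1: "To describe the proportion of Pfizer-BioNTech bivalent mRNA COVID-19/influenza vaccines that are concomitantly administered". It names no denominator.

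**The concern.** Because group membership is read from claims, a same-day recipient with one unclaimed dose is not lost. That person leaves Group 1 and enters the group it is compared with. The section 9.9 sentence reads as containment, yet a contaminated comparator affects every HR, and Group 1 itself becomes too small.

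Two results are at stake. First, the only success benchmark in the plan is an upper bound of 1.15. If same-day administration were truly worse, mixing same-day patients into the comparator would lower the estimated HR and make non-inferiority easier to claim. Second, the count of concomitant administrations in Objective 1 falls, while the denominator may or may not fall with it.

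**Working it through.** **1. The plan's own figure.** Events = (1.960 + 0.842)² / [p(1−p)(ln 1.15)²]. With p = 0.63 this gives 1,724, and with p = 0.23 it gives 2,269. Both match section 9.5, so the same model is used below.

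**2. Inputs.** From Table 5:

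| Age | Group 1 | Group 2 | Group 3 |
|---|---|---|---|
| 65+ | 382,806 | 225,842 | 1,351,093 |
| 18-64 | 244,864 | 144,695 | 772,418 |

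Event proportions from section 9.5: COVID-19 composite 65+ 0.56%; COVID-19 outpatient 18-64 1.47% and 65+ 1.77%; influenza composite 65+ 0.3%. The documents give no missed-claim rate. I **assume** that a share m of true same-day recipients lack one of the two claims, with m = 5% or 10%.

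**3. From missed claims to contamination.** Observed Group 1 is (1−m) of the true same-day group, so the number moved is G1·m/(1−m). The contaminated share of the comparator is q = G1·m/[(1−m)·G_comparator].

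- Influenza claim missing, 65+, m = 10%: 382,806 × 0.1/0.9 = 42,534; divided by 225,842, q = 18.8%. At m = 5%: 20,148/225,842 = 8.9%.
- The same for 18-64: 12,888/144,695 = 8.9% and 27,207/144,695 = 18.8%.
- COVID-19 claim missing, 65+: 20,148/1,351,093 = 1.5% and 42,534/1,351,093 = 3.1%.

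Group 1 is larger than Group 2 and much smaller than Group 3, so the same m is magnified in one comparison and diluted in the other.

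**4. From contamination to the HR.** With rare events and missingness unrelated to outcome, observed HR = HR/(1 − q + q·HR). At a true HR of 1 this equals 1 for any q. At 0.80 with q = 20% it is 0.833, so benefit is understated. At 1.15 it is shown below.

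**5. False non-inferiority at a true HR of 1.15.** Probability = Φ(ln(1.15/HR_obs)/SE − 1.96), with SE = 1/√(D·p(1−p)), D = Table 5 total × event proportion, and p = the Table 5 share in Group 1. The nominal value is 2.5%.

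| Comparison and endpoint | D | SE | m | q | HR_obs | False NI |
|---|---|---|---|---|---|---|
| vs COVID alone, composite 65+ | 3,408 | 0.0355 | 5% | 8.9% | 1.135 | 5.6% |
| | | | 10% | 18.8% | 1.118 | 12.0% |
| vs COVID alone, outpatient 18-64 | 5,727 | 0.0274 | 5% | 8.9% | 1.135 | 7.0% |
| | | | 10% | 18.8% | 1.118 | 17.3% |
| vs COVID alone, outpatient 65+ | 10,773 | 0.0199 | 5% | 8.9% | 1.135 | 9.8% |
| | | | 10% | 18.8% | 1.118 | 28.7% |
| vs Flu alone, composite 65+ | 5,202 | 0.0334 | 5% | 1.5% | 1.147 | 2.9% |
| | | | 10% | 3.1% | 1.145 | 3.4% |

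**6. Objective 1, 65+.**

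- *Among bivalent recipients:* observed 382,806/608,648 = 62.9%. If same-day recipients lack the influenza claim, the denominator is unchanged and the truth is 402,954/608,648 = 66.2% (m = 5%) or 425,340/608,648 = 69.9% (m = 10%).
- *Among influenza recipients:* observed 382,806/1,733,899 = 22.1%. If 10% lack the COVID-19 claim, the truth is 425,340/1,733,899 = 24.5%, so uptake is understated. If influenza claims are missed equally in Groups 1 and 3, there is no bias. If 2% of same-day and 10% of influenza-alone doses are missed, the truth is 390,618/(390,618 + 1,501,214) = 20.6%, so uptake is overstated, because a wholly unclaimed influenza-alone recipient never enters the cohort.

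**The case against.** The strongest reply is that the sentence is correct as far as it goes. Group 1 needs two claims, so a missing claim cannot put a wrong patient into it; the misclassified patients do sit in the single groups. That stands. The sentence is incomplete about the consequence, not false about the location.

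Several stronger readings are tempting, and the documents do not support them:

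- *Unclaimed vaccines always favour non-inferiority.* Only if the true HR exceeds 1. At the planned HR of 1 nothing moves, and below 1 the bias hides benefit.
- *Every missed vaccine pulls the HR toward 1.* Only doses given on the same day as the claimed one do. An unclaimed dose on another day makes the patient a sequential recipient who escapes the censoring in section 9.3.3, and the direction is then uncertain. It is also unknown if missing claims relate to health or care-seeking.
- *Both comparisons are equally exposed.* For 20% of Group 3 (65+) to be truly same-day, about 41% of same-day recipients would have to lack the COVID-19 claim: 0.2 × 1,351,093 = 270,219; 270,219/(382,806 + 270,219) = 41%.
- *Objective 1 is always understated.* That depends on the denominator, which section 8 does not name.
- *The plan contains no analysis of this.* Parts of sections 9.3 and 9.7 are redacted, so only the visible text can be judged.

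It is also fair to say that section 9.7 states no non-inferiority test. The margin appears only in section 9.5, but it is the only benchmark the plan gives for reading the HRs.

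**Conclusion.** The concern holds in a limited form. Unclaimed same-day doses affect the HRs and the Objective 1 proportion, and the visible plan gives neither direction nor analysis. The effect is material for Same day vs COVID alone. At assumed missed-claim rates of 5% and 10%, false non-inferiority at the margin is about 5.6% and 12.0% for the 65+ COVID-19 composite, and about 7.0% and 17.3% for the 18-64 COVID-19 outpatient endpoint, instead of 2.5%. The younger group matters because section 9.9 itself suspects more missed influenza claims there, and section 9.5 counts that endpoint as adequately sized. For Same day vs Flu alone the effect is small (3.4% at a 10% rate). Among bivalent recipients aged 65+, uptake is understated by about 3 to 7 percentage points.

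These figures rest on assumed rates, a true HR of exactly 1.15, rare events, missingness unrelated to outcome, and unweighted standard errors. The planned inverse probability weighting could change the standard errors.

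**What to change.** 1. In section 9.9, replace the closing sentence on the single-vaccine groups. State that unclaimed same-day doses move patients from Group 1 into the comparator. If missingness is unrelated to outcome, the HR then moves toward 1: this favours non-inferiority if the true HR exceeds 1, has no effect at 1, and hides benefit below 1. State that the effect is larger against COVID alone than against Flu alone, and that unclaimed doses on other days escape censoring with uncertain direction.
2. In section 8 or 9.7, name the denominator or denominators for Objective 1 and state the direction of bias for each.
3. In section 9.7, add a quantitative bias analysis by age group over a stated range of missed-claim rates, for example 2% to 20% of true same-day recipients. Report the corrected HR and upper bound, mainly for Same day vs COVID alone, and the corrected Objective 1 proportion.

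A restriction to patients with a prior vaccine claim could be run with covariates already in Table 4 (such as "One claim (NDC or CPT) for influenza vaccine of any type measured between" the prior-season dates), but only as optional and exploratory. A prior claim does not prove that this season's doses are captured, and the restriction may enrich for habitual vaccinees who were vaccinated elsewhere this time.

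The cost is a few sentences and one small table. The downside is that the table rests on assumed rates and must be labelled so.

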9.10. Other Aspects

Not applicable.

10. PROTECTION OF HUMAN SUBJECTS

10.1. Patient Information

This study involves data that exist in anonymized structured format and contain no patient personal information.

10.2. Patient Consent

As this study involves anonymized structured data, which according to applicable legal requirements do not contain data subject to privacy laws, obtaining informed consent from patients by Pfizer is not required.

10.3. Institutional Review Board (IRB)/Independent Ethics Committee (IEC)

This study uses de-identified data. As such this study will be submitted to an IRB for exemption under category 4, pursuant to the terms of the US Department of Health and Human Service's Policy for Protection of human Subjects at 45 C.F.R 46.104(d).

10.4. Ethical Conduct of the Study

The study will be conducted in accordance with legal and regulatory requirements, as well as with scientific purpose, value and rigor and follow generally accepted research practices described in Guidelines for Good Pharmacoepidemiologic Practices (GPP),²⁰ Good Practices for Outcomes Research issued by the International Society for Pharmacoeconomics and Outcomes Research (ISPOR),²¹ and Food and Drug Administration (FDA) Guidance for Industry: Good Pharmacovigilance Practices and Pharmacoepidemiologic Assessment.²²

11. MANAGEMENT AND REPORTING OF ADVERSE EVENTS/ADVERSE REACTIONS

This study involves data that exist as structured data by the time of study start. In these data sources, individual patient data are not retrieved or validated, and it is not possible to link (ie, identify a potential association between) a particular product and medical event for any individual. Thus, the minimum criteria for reporting an adverse event (AE) (ie, identifiable patient, identifiable reporter, a suspect product, and event) cannot be met.

12. PLANS FOR DISSEMINATING AND COMMUNICATING STUDY RESULTS

For all publications relating to the study, Pfizer will comply with recognized ethical standards concerning publications and authorship, including Section II - "Ethical Considerations in the Conduct and Reporting of Research" of the Uniform Requirements for Manuscripts Submitted to Biomedical Journals, <http://www.icmje.org/index.html#authorship>, established by the International Committee of Medical Journal Editors.

In the event of any prohibition or restriction imposed (eg, clinical hold) by an applicable competent authority in any area of the world, or if the party responsible for collecting data from the participant is aware of any new information which might influence the evaluation of the benefits and risks of a Pfizer product, Pfizer should be informed immediately.

ANNEX 1. LIST OF STAND ALONE DOCUMENTS

None.

PFIZER CONFIDENTIAL

